## PROTOCOL SUMMARY

### **1. IDENTIFICATION OF THE PROTOCOL**

Sponsor protocol code: LoViReT II  
Version/Date: Version 5, 19/01/2017

### **2. TITLE OF THE STUDY**

Low Viral Reservoir in Treated Subjects (LoViReT) - Phase II: Predictors of Extremely Low HIV-1 DNA Reservoir in Subjects Initiating cART during Chronic Infection

### **5. RESEARCH ETHICS COMMITTEE WITH DRUGS**

The IRB at Univ. Hospital 'Germans Trias i Pujol'.

### **6. CENTER WHERE THE STUDY WILL BE CARRIED OUT**

Univ. Hospital 'Germans Trias i Pujol'

### **7. JUSTIFICATION AND RELEVANCE OF THE STUDY**

Antiretroviral therapy (ART) for HIV-1 significantly reduces the morbidity and mortality associated with AIDS events. However, it fails to eliminate the virus that persists in the form of latent infection in the cell reservoirs, which implies a rapid rebound of viral load if the treatment is interrupted. Currently, there is a wide variety of strategies that aim to reduce the viral reservoir, with the ultimate goal of reducing it to undetectable levels.

To date, only two strategies have been successful in meeting this goal: the early start of antiretroviral treatment and allogeneic stem cell transplantation in the Berlin patient. However, despite having an undetectable latent reservoir, patients suffer a viral rebound within a few months after stopping treatment (except in the Berlin patient). These results show that an undetectable reservoir of HIV-1 does not mean a cure for the virus. Therefore, there is a need to understand the nature of HIV reservoirs that must be eliminated to achieve a cure.

Thus, LoViReT patients are the perfect model to: I) discover the places where the virus persists in the body despite the apparent eradication of HIV in the blood; II) elucidate

the mechanisms by which a patient can maintain extremely low levels of HIV-1 DNA despite having started ART during chronic HIV-1 infection; and III) develop a predictive technique that can anticipate viral rebound before discontinuation of antiretroviral therapy.

## **8. DESIGN**

Unicentric, case-control, observational clinical study.

## **9. PRINCIPAL OBJECTIVE**

The main objective of the LoViReT project is to identify and characterize the most relevant factors involved in maintaining an extremely low viral reservoir in an exceptional group of patients treated during the chronic phase of infection with antiretroviral therapy. Among these factors we would include both virological factors (viral tropism, complete genome, replicative capacity ...), immuno-genetic factors (HLA, CTL response, plasma neutralization capacity, phenotype of lymphocyte populations, cell activation, transcriptomics ...) and clinical factors (progression clinic, mode of transmission, age, therapeutic picture, sex ...).

## **10. EXPERIMENTAL DRUG AND CONTROL. DOSAGE, PHYSICAL FORM, ROUTE OF ADMINISTRATION, THERAPEUTIC GROUP**

Does not apply

## **11. PRIMARY ENDPOINT**

The primary endpoint is to study the cell-associated HIV DNA, the level of CD4 + T cells from both peripheral blood and associated lymphoid tissues (rectum and lymph node) plus clinical parameters, factors immuno-genetic and the virus itself.

## **12. STUDY POPULATION AND TOTAL NUMBER OF PATIENTS**

### **12.1. Selection criteria:**

#### **Inclusion criteria**

- $\geq 18$  years of age;
- voluntarily signed informed consent;
- proven HIV-1 infection;
- on stable cART regimen for at least 3 years;
- HIV-RNA  $<50$  copies/mL during the last 3 years prior to the study (blips under 200 copies/ml are permitted in 5% of determinations during last 3 years);
- proviral HIV-DNA  $<50$  copies/million PBMCs by using the ultrasensitive BioRad residual ddPCR quantification platform.

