#### **Exclusion criteria**

- In women, pregnancy or breastfeeding.
- cART discontinuation since the moment of the previous screening to the date of Visit #1.
- HIV-RNA above 200 copies/mL since the moment of the previous screening to the date of Visit #1

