### **12.2. Total number of participants:**

This study is expected to include a total of 86 HIV-infected patients of which 43 patients will come from the LoViReT I cohort, forming the experimental group and the other 43 patients will be shortlisted to form the control group.

The patients of the control group will be included according to the reason 1 control: 1 experimental, in a paired way by age, sex and clinical profile.

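### The title's restriction to cART started in chronic infection is not carried into the eligibility criteria, so the 43 controls have no stated filter on phase of infection at treatment start

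*Combined protocol and SAP*

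**What the plan says.** The title (Section 2) sets the scope as "Predictors of Extremely Low HIV-1 DNA Reservoir in Subjects Initiating cART during Chronic Infection". Section 7 describes the LoViReT patients as keeping very low HIV-1 DNA "despite having started ART during chronic HIV-1 infection", and Section 9 describes the same low-reservoir group as treated in the chronic phase.

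Section 12.1 lists six inclusion and three exclusion criteria. Two concern cART. One asks that participants be "on stable cART regimen for at least 3 years"; the other excludes "cART discontinuation since the moment of the previous screening to the date of Visit #1". The reservoir criterion is a proviral HIV-DNA below 50 "copies/million PBMCs by using the ultrasensitive BioRad residual ddPCR quantification platform", and it is not assigned to either group.

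Section 12.2 states that "43 patients will come from the LoViReT I cohort, forming the experimental group" and that "the other 43 patients will be shortlisted to form the control group". Controls are chosen one to one, "in a paired way by age, sex and clinical profile".

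**The concern.** A case-control comparison is interpretable when the controls come from the population that gave rise to the cases. Here that population is people who started cART in chronic infection. If the cases all meet that condition and the controls need not, timing of treatment can differ between the groups through selection alone.

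The protocol itself explains why timing matters. Section 7 names early treatment as one of just two approaches that have reached an undetectable reservoir, so on its own premise timing is linked to the characteristic that defines a case. A difference in a virological, immuno-genetic or clinical factor could then partly reflect when treatment began, and not a mechanism that keeps the reservoir low after late treatment. Early-treated controls would also lie outside the population that the title names.

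A second, separate problem sits in the same list. If the HIV-DNA criterion is applied to every participant, as its placement implies, controls must have the low reservoir that is supposed to distinguish the cases.

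**Working it through.** No figure in the plan is in dispute, so the check is a reading of the eligibility text with simple counts.

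**Step 1: group sizes.** Section 12.2 gives 43 cases + 43 controls = 86. Controls are 43/86 = 50% of participants and, with one-to-one pairing, one member of every pair.

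**Step 2: the criteria in Section 12.1.**

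| Criterion | Type | Mentions cART | Addresses phase or timing of cART start |
|---|---|---|---|
| Age | Inclusion | No | No |
| Consent | Inclusion | No | No |
| HIV-1 infection | Inclusion | No | No |
| Stable cART, 3 years or more | Inclusion | Yes | No |
| HIV-RNA suppression | Inclusion | No | No |
| HIV-DNA below 50 | Inclusion | No | No |
| Pregnancy or breastfeeding | Exclusion | No | No |
| cART discontinuation since screening | Exclusion | Yes | No |
| HIV-RNA above 200 since screening | Exclusion | No | No |

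Totals: 6 + 3 = 9 criteria; 2 mention cART; 0 address when it was started. The 3-year rule is a minimum duration. A person treated soon after infection and a person treated years later both meet it once 3 stable years have passed.

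**Step 3: other text that could supply the filter.**

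- Cases: Section 12.2 draws them from LoViReT I, and Sections 7 and 9 describe that low-reservoir group as treated in chronic infection. This is description and not a criterion, but it covers the 43 cases.
- Controls: Sections 7 and 9 do not describe them. Only the title remains.
- Matching: three terms are named. Age and sex are explicit. Clinical profile is defined nowhere and may or may not include phase at cART start.
- Prior screening: the exclusion criteria refer to one, but its rules are not given.

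**Step 4: how the HIV-DNA criterion changes the consequence.**

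- *Cases only, controls required to have larger reservoirs.* On the premise of Section 7, early-treated patients are less likely to qualify as controls. They are filtered in part, not fully.
- *Cases only, no reservoir rule for controls.* Neither phase nor reservoir level is restricted for controls.
- *All participants, the literal reading.* On the same premise, early-treated patients are more likely to qualify, and the low-versus-higher contrast is lost whatever the phase at start.

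The documents do not settle which holds. None of the three excludes early-treated controls.

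**Step 5: effect on the power statement.** Section 13 works from sample size, standardised effect and significance level. A criterion on phase enters none of these, so there is no revised power figure to report.

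**The case against.** The strongest reply is that Section 12.1 was probably written for the cases. The HIV-DNA limit fits the low-reservoir group, and Section 12.2 describes controls separately, as shortlisted and paired. On that reading, a count of zero in nine says little about controls. This has force, but it does not close the gap: the controls would then have no eligibility rules at all in this document.

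It can also be said that the title governs, so the restriction is stated and only needs to be made operational. That is fair as to intent. A title does not, however, tell screening staff how to classify a candidate or what to do when timing is undocumented.

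Clinical profile might include phase at cART start. Section 9 gives examples of clinical factors, among them progression and treatment history, which could cover it. But that list is open-ended, nothing ties it to the matching term, and an undefined term is not a filter.

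Controls with larger reservoirs would seldom be early-treated. This stands in part: it makes the effect smaller on the reading in which the study works as intended, but the document does not state that requirement.

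Finally, the text is headed a protocol summary, and the definition may be held elsewhere. That cannot be ruled out, and it limits the claim to what this document says.

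A reader might go further and infer that the comparison is confounded by treatment timing, or that the sponsor means to enrol early-treated or low-reservoir controls. The documents do not support either inference. They give nothing on the pool from which controls are drawn, and the study's aim suggests that the HIV-DNA wording is a drafting slip and not a decision.

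**Conclusion.** The point holds as an omission in the eligibility text. The chronic-infection restriction is in the title but in 0 of 9 criteria. It is supplied by description for the 43 cases and by nothing operational for the 43 controls, who are 50% of the sample. As written, early-treated patients are eligible as controls, and case-control differences could partly reflect treatment timing.

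That bias is possible, not shown. Its size and direction cannot be derived from the documents, and it is smaller if controls must have larger reservoirs. Its relevance rests on the statement in Section 7 that early treatment can bring the reservoir to undetectable levels.

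The HIV-DNA point is separate and does not depend on phase: applied literally to controls, the criterion removes the contrast the study needs. Confidence is high in what the text omits, subject to the possibility that a fuller protocol contains it. The text should be corrected, because the correction is cheap and the selection of controls depends on it.

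**What to change.** Three edits are needed.

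1. In Section 12.1, add for both groups that cART was started during chronic infection. Give an operational definition, using the one from LoViReT I if it exists, and check it against the clinical record. State a rule for candidates whose timing is undocumented.
2. In Section 12.1, limit the HIV-DNA criterion (below 50 copies per million PBMCs) to cases, and require that controls do not meet it.
3. In Section 12.2, list the variables that make up clinical profile. Close matching on time to cART within chronic infection is not needed: treatment history is among the factors that Section 9 sets out to study, and leaving this timing unmatched keeps it open to analysis.

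The cost is a few lines of text and a chart check. Some shortlisted controls may become ineligible; the documents do not allow an estimate of how many. Early and chronic-phase starters could no longer be compared, but the title already implies that. If a fuller protocol holds the definition, it only needs to be copied in.

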## **13. STATISTICAL ANALYSIS**

The absence of previous data for the factors to be analyzed makes it impossible to make an accurate study of the statistical power and the required sample size. However, we can make a rough estimate of the power by reference to the use of non-parametric tests and the measurement of the Cohen effect size (d), defined as the difference between the means divided by the standard deviation of the data.

Although the size of the feasible sample does not allow us to achieve enough power to observe small effects ( $d = 0.2$ ), with a sample size of 40 patients per group (a total N of 80) we reach a power of about 60% to average effects  $D = 0.5$ ) and more than 90% for large effects ( $d = 0.8$ ). With a sample size of 20 patients per group (N = 40) we reach a power of 70% for large effects. The calculations have been made considering a significance level of 0.05 and two tails.

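### Selecting cases on HIV DNA per million PBMCs by itself tends to lower their CD4+ share, so measures that track that share can emerge as false factors

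*Combined protocol and SAP*

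**What the plan says.** - Section 12.1 requires proviral HIV DNA below 50 "copies/million PBMCs by using the ultrasensitive BioRad residual ddPCR quantification platform". Neither the inclusion nor the exclusion criteria mention CD4 count, CD4 % or HIV DNA per CD4+ cell.
- Section 12.2: "43 patients will come from the LoViReT I cohort, forming the experimental group". Another 43 controls are chosen 1:1, "in a paired way by age, sex and clinical profile". Clinical profile is not defined.
- Section 9 lists the candidate factors. Among the immuno-genetic ones are "phenotype of lymphocyte populations, cell activation, transcriptomics".
- Section 11 gives the primary endpoint as "the cell-associated HIV DNA, the level of CD4 + T cells from both peripheral blood and associated lymphoid tissues", together with clinical, immuno-genetic and viral parameters.
- Section 13 refers to non-parametric tests and a rough power estimate. It describes no normalisation to CD4+ cells and no adjustment for CD4+ share.

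The under-50 criterion is listed for all participants, and no separate control threshold is given. That it defines the cases is inferred from sections 7 and 12.2.

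**The concern.** The selection variable is a product of two things: how much HIV DNA the CD4+ T cells carry, and what proportion of PBMCs are CD4+ T cells. The first is the reservoir that the study wants to explain. The second is a denominator effect, yet it is also the kind of quantity that a lymphocyte phenotyping panel reports.

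Comparing cases and controls on a component of the selection variable gives a difference built in by selection. The study's purpose is to name factors that maintain a low reservoir. A lower CD4 % or CD4/CD8 ratio in cases could be reported as such a factor when it only reflects the unit of the cut-off. The bias runs one way, towards a lower share in cases. It can therefore create a false finding in that direction or hide a true one in the other.

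**Working it through.** **The plan's own power figures.** Inputs from section 13: 40 or 20 per group, d = 0.5 or 0.8. "The calculations have been made considering a significance level of 0.05 and two tails". With power ≈ Φ(d·√(n/2) − 1.96):

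- n = 40, d = 0.5: Φ(2.236 − 1.96) = 60.9% (t-test 59.8%); stated about 60%.
- n = 40, d = 0.8: Φ(3.578 − 1.96) = 94.7% (t-test 94.2%); stated above 90%.
- n = 20, d = 0.8: Φ(2.530 − 1.96) = 71.6% (t-test 69.3%); stated 70%.

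These reproduce and are not in dispute. They show which effect sizes the study can detect.

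**The identity.** Let f be the CD4+ share of PBMCs and c the HIV DNA copies per million CD4+ T cells. Taking the HIV DNA to lie in CD4+ T cells (an assumption), copies per million PBMCs = f × c. The cut-off f × c < 50 is the same as c < 50/f:

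| f (assumed) | Equivalent cut-off per million CD4+ T cells |
|---|---|
| 10% | 500 |
| 20% | 250 |
| 30% | 167 |
| 40% | 125 |
| 50% | 100 |
| 60% | 83 |

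A patient with c = 150 reads 150 × 0.20 = 30 (below the cut-off) at f = 20%, and 150 × 0.50 = 75 (above it) at f = 50%. The switch is at 50/150 = 33%. At c = 1000 the share would have to fall below 50/1000 = 5%.

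**Size of the induced gap.** The documents give no distribution for f or c, so every input here is assumed. Large populations were simulated with f and c independent, so the true effect of f on the reservoir is zero. Cases are those below the cut-off, controls are everyone else, and there is no matching.

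- *Main range:* f mean 35–40%, SD 8–10%; log10 c SD 0.5–0.7; 5–20% of patients below the cut-off. Cases have lower f by d of about 0.23 to 0.65. At 43 per group, √(43/2) = 4.637. The chance of p < 0.05 runs from Φ(0.23 × 4.637 − 1.96) = Φ(−0.89), about 19%, to Φ(0.65 × 4.637 − 1.96) = Φ(1.05), about 85%. The t-test gives about 18 to 85%. The nominal rate is 5%.
- *One worked scenario:* median c 1000, log10 SD 0.5, f mean 30%, SD 8%. Mean f is 25.8% in cases and 30.3% in non-cases, d = 0.56, significant in about 72% of studies. About 27% of cases lie above 167 copies per million CD4+ T cells, the cut-off equivalent at mean f.
- *Wider range:* median c 500–2000, log10 SD 0.4–0.7, f mean 30%, SD 5–10%. d runs from 0.18 to 1.46, always in the same direction.
- *Control check:* if cases are defined per million CD4+ T cells, the induced gap is about zero.

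**The case against.** Several points on the other side stand and limit the claim.

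- **Section 11 is ambiguous.** It may mean HIV DNA measured in CD4+ T cells from blood, rectum and node. CD4 level is then not a compared quantity, and the per-CD4 measure is at least partly planned already. A reader might infer that CD4 level is certainly a primary endpoint; the wording does not settle that. On this reading the endpoint unit differs from the selection unit, and the phenotype factors in section 9 are still compared.
- **Most factors are not tied to group.** A reader might infer that all immune-phenotype results are compromised. The identity reaches only measures that follow the CD4+ share of PBMCs. HLA, viral tropism, viral genome, replicative capacity and subsets measured within CD4+ cells are not directly affected. Activation or clinical progression are affected only so far as they correlate with the share.
- **A low share cannot make just anyone a case.** It decides case status only in a band, about 83 to 500 copies per million CD4+ T cells for shares of 60% down to 10%.
- **Matching may help.** If clinical profile includes CD4 %, the gap largely disappears. Section 12.2 does not say so, and one sentence there could close most of the point.
- **The percentages are illustrative.** They use assumed distributions and unmatched controls, so 18 to 85% is not this study's false-positive rate. If the under-50 criterion really applied to controls too, the calculation would not describe the design.

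That the study is observational, with power described as rough, does not answer the point: the gap comes from selection and not from sample size.

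**Conclusion.** The concern holds in a limited form. Defining cases per million PBMCs builds in a tendency to a lower CD4+ share among them, and nothing stated in the plan removes it. The direction follows from algebra, given that HIV DNA lies in CD4+ T cells and that the criterion defines the cases. The size depends on assumptions: d of about 0.23 to 0.65 in the main range without matching. That includes the d = 0.5 for which section 13 claims about 60% power.

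At risk is the interpretation of CD4 %, the CD4/CD8 ratio, lineage proportions within "phenotype of lymphocyte populations", and CD4 level if section 11 means that. A higher CD4+ share in cases could not be explained by the artefact, which works against it. A reader might also conclude that the cohort or its threshold is invalid. The documents do not support that, because the problem can be handled in the analysis.

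**What to change.** Keep the cohort and the threshold, and add the following to section 13:

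1. Express blood HIV DNA per million CD4+ T cells as well as per million PBMCs, using the CD4+ share of the same PBMC sample, and compare the groups on that scale. Phenotyping is already planned, but the plan should confirm that this share is recorded.
2. Repeat the comparisons of other phenotype, activation and clinical factors with adjustment for CD4+ share.
3. State in advance that a lower CD4+ share in cases will not be read as explanatory from the case-control contrast. An analysis adjusted for CD4+ share cannot test the share itself. Assess it only through its association with HIV DNA per million CD4+ T cells, in cases and controls together. Within cases alone, the cut-off on the product forces the two components into a negative relation.
4. Say in section 12.2 whether clinical profile includes CD4 % or CD4 count, and clarify the wording of section 11.

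Restricting to cases that are also low per million CD4+ T cells should not be the main remedy. With the cut-off converted at the mean share, it leaves a residual d of about 0.12 to 0.26 and loses 9 to 33% of cases under the same assumptions.

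The cost is a second, slightly less precise analysis to report, with little or no new data if the CD4+ share is recorded.

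### A low ddPCR reading sets low-reservoir status with no stated check for poorly bound virus, while the viral genome is itself a candidate explanatory factor

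*Combined protocol and SAP*

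**What the plan says.** Section 12.1 (Inclusion criteria) requires proviral HIV DNA under 50 "copies/million PBMCs by using the ultrasensitive BioRad residual ddPCR quantification platform". It names no target region, second target, primer or probe check, or restriction on viral subtype.

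Section 9 aims to "identify and characterize the most relevant factors involved in maintaining an extremely low viral reservoir". The first class of factor it names is "virological factors (viral tropism, complete genome, replicative capacity", among others. Section 11 places in the primary endpoint "the cell-associated HIV DNA, the level of CD4 + T cells from both peripheral blood and associated lymphoid tissues" and, further on, "plus clinical parameters, factors immuno-genetic and the virus itself".

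Section 8 describes a "Unicentric, case-control, observational clinical study". Under Section 12.2, "43 patients will come from the LoViReT I cohort, forming the experimental group". An equal number of controls is to be selected and paired 1:1 on age, sex and clinical profile; viral subtype and sequence are not named as matching factors. Section 13 contains only a power discussion. It gives no rule for assay misclassification and no specific test for the genome data.

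**The concern.** A PCR count depends on how much template is present and on how well the primers and probe bind it. Choosing people for a very low reading therefore selects both those with few proviruses and those whose virus is under-read. If viral sequence is then examined as a reason for being a case, the comparison partly tests the selection rule.

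Two errors could follow. False cases would dilute real immune and clinical differences. A sequence feature at the assay target, or linked to it, could be reported as a factor that maintains a low reservoir when it reflects only detection. The error is systematic, so repeating the same assay would not remove it.

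**Working it through.** **The plan's own figure.** Section 13 gives about 60% power for d = 0.5 with 40 per group, two-sided 0.05. A two-sample t-test gives 59.8%, so the figure reproduces. It does not bear on misclassification, but the same formula prices the fix: 63.0% with 43 per group, 59.8% with 40, 54.1% with 35.

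**Inputs from the documents.** Cut-off 50 copies/million PBMCs, so c = log10(50) = 1.70; 43 cases and 43 controls; two-sided 0.05.

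**Assumed inputs.** The documents give neither the reservoir distribution nor the assay target.
- True log10 HIV DNA is normal, with mean μ of 2.5 to 3.0 and SD σ of 0.5 to 0.6.
- A share q of 1% to 5% carries poorly bound virus, unrelated to true reservoir size.
- Carriers are under-read by k log10 units, with k from 0.5 (about threefold) to 1 (tenfold).
- Controls read 50 or above. Section 12.1 gives no separate HIV-DNA rule for controls, so this too is an assumption.

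**Formulas.** With F(x) = Φ((x − μ)/σ):
- share reading low: R = q·F(c + k) + (1 − q)·F(c)
- false share of cases: q·[F(c + k) − F(c)] / R
- carriers among cases: q·F(c + k) / R
- carriers among controls: q·[1 − F(c + k)] / (1 − R)

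**Worked example: μ = 2.7, σ = 0.5, q = 0.02, k = 0.5.**
- F(1.70) = Φ(−2) = 0.02275 and F(2.20) = Φ(−1) = 0.15866.
- R = 0.02 × 0.15866 + 0.98 × 0.02275 = 0.02547.
- False share = 0.02 × 0.13591 / 0.02547 = 10.7%, about 5 of 43.
- Carriers among cases = 0.003173 / 0.02547 = 12.5%.
- Carriers among controls = 0.02 × 0.84134 / 0.97453 = 1.7%.

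**Chance of a significant association.** This is Fisher's exact test at 43 v 43, summed over the two binomial distributions. The mismatch itself is the factor tested, pairing is ignored, and there is no multiplicity correction.

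| μ, σ | q | k | False cases | Carriers, cases v controls | p < 0.05 |
|---|---|---|---|---|---|
| 2.5, 0.6 | 1% | 0.5 | 2.3% | 3.3% v 0.8% | 0.2% |
| 2.7, 0.5 | 1% | 0.5 | 5.6% | 6.6% v 0.9% | 4.4% |
| 2.7, 0.5 | 2% | 0.5 | 10.7% | 12.5% v 1.7% | 28% |
| 2.7, 0.5 | 2% | 1 | 29.6% | 31% v 1.0% | 99% |
| 3.0, 0.5 | 5% | 1 | 74% | 76% v 3.7% | about 100% |

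The first and last rows are the extremes of the assumed range.

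**A second model.** This one assumes directly the share truly below 50 (5% to 20%), carrier prevalence (1% to 10%) and the probability that a carrier truly at or above 50 reads below it (25% to 100%). False cases run from 1% to 66%, and the chance of a significant result from about 0% to 100%. At 1% prevalence, with that probability at most 50%, the chance is at most 19%.

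**Smallest split that reaches significance.** If no control carries the feature, 5 of 43 cases gives p = 0.055 and 6 of 43 gives p = 0.026.

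**The case against.** The strongest reply is that the gap is read from a protocol summary. One eligibility line names a platform, and a platform is not a primer set. The assay may read several regions or be matched to subtype, and such details may sit with the earlier LoViReT I cohort from which the cases come. This stands: it makes the mechanism conditional, and one sentence naming the target region(s) could largely settle it.

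A reader might infer more than the documents support, in three ways.
- That a single region is read. Section 12.1 does not say so.
- That a between-group genome test is specified. It is a reasonable reading of Sections 8, 9 and 12.2 together, but Section 13 names no such test.
- That rectal and lymph-node results would repeat the error and seem to confirm it. Section 11 names no tissue assay, so this is only a possibility.

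The size is also open to challenge. Every driving input is assumed, and at the mild end a false viral factor is unlikely. The Fisher calculation is favourable to the concern: a linked marker such as subtype would show a weaker association than the mismatch itself, and multiplicity correction across a genome would lower rejection further. Both points stand. Against them, the exact test is very conservative for rare features. With no artefact it rejects 0.5% of the time at 5% prevalence and almost never at 1%, so 4.4% is small but still well above what chance alone would give.

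Finally, sequencing is hardest where HIV DNA is lowest, so true cases are the likeliest to go unchecked. The fix can report this limit but not remove it.

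**Conclusion.** The point holds as a conditional risk. The plan selects on an assay signal, states no check that a low signal means few proviruses, does not match on viral sequence, and lists the viral genome as a candidate explanation. If the assay has one target, or targets that share mismatches, cases would be enriched for poorly bound virus.

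The documents do not support the stronger conclusion that cases are in fact misclassified, or that a genome finding would be an artefact. The ranges in the working are too wide to say whether the problem is trivial or serious, and they rest on the assumed reservoir distribution, mismatch prevalence and degree of under-reading. The case for acting is that the check is cheap, and that without it a reported genome or subtype association could not be told apart from detection failure. It is a change to consider, with low-to-medium confidence.

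**What to change.** Add to the analysis plan, using the genome sequences already listed and naming the ddPCR target region(s) so that the check can be done:

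1. Check the ddPCR primer and probe sites in all cases and all controls by one mismatch rule fixed in advance.
2. Repeat the main case-control comparisons without any pair in which either member has a mismatch. The rule should apply to both groups alike.
3. Mask the assay target positions in the viral-genome comparison, and report any genome or subtype association with and without the mismatched pairs. Masking alone does not remove signal from linked positions.
4. Report by group how many participants could not be sequenced at those sites, since this is likelier in truly low-reservoir cases.

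The cost is protocol wording and a check on planned data, with no added recruitment or visits. The sensitivity analysis loses pairs: power at d = 0.5 falls from 63% with 43 per group to 60% with 40 and 54% with 35. Cases that cannot be sequenced at the assay sites stay unchecked.
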